on them. Parents also learn to understand each other's perspectives such that actions which might previously have been attributed to hostile motivations are viewed in a more balanced way. The insights that parents glean into each other's and their child's experiences lead to a reduction in conflict and more adaptive ways to manage disagreements. A small-scale random allocation feasibility study compared MBT-PP to treatment as usual (a Parents' Group, 'PG') and found encouraging support for this (Hertzmänn et al., 2016; Hertzmänn et al., 2017). Thirty parents (15 pairs of separated co-parents who were entrenched in chronic and intense conflict over their children), completed quantitative measures and qualitative interviews (pre and post-intervention) to explore several outcome variables. Both intervention groups (MBT-PP and PG) showed statistically significant improvements in reported: 1) expressions of anger towards the ex-partner; 2) levels of stress and depression; and 3) behavioural and emotional difficulties experienced by their children. Furthermore, in both groups, attitudes towards the ex-partner improved. Following MBT-PP in particular, parents' descriptions of their ex-partners became less polarised and they were more able to accept that their co-parent was likely experiencing similar feelings and motivations to themselves (Hertzmänn et al., 2016; Hertzmänn et al., 2017). Importantly, whilst the study failed to detect a significant difference in the parents' ability to mentalise according to the quantitative measures, the qualitative findings suggested that nuanced shifts in this had occurred. The authors posited that the study may have only detected the first part of a process of change, with a larger, longer-term study better able to establish what was going on (Hertzmänn et al., 2016). Overall, the study showed promise and suggested that a full-scale RCT would be warranted. Recently, Tavistock Relationships have provided MBT-PP as part of the Department of Work and Pensions' Reducing Parental Conflict programme, delivering MBT-PP to over 1,000 parents in 2022.

Evaluation Design

The current evaluation of MBT-PP is a pragmatic randomised controlled trial with internal pilot study. All referrals will be randomised to receive either MBT-PP or Treatment as Usual (TAU).

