The updated power analyses presented here illustrate that, even with fewer CYP per family than initially estimated, a smaller sample of families is likely to be sufficient sensitivity to detect an MDES of 0.20 sds or higher than was estimated at protocol. With 250 families (and 350 CYP), the MDES estimate is 0.17 sds. With an attrition rate of 10%, assuming attrition was random, the indicative MDES estimate is 0.18 sds. With an attrition rate of 20%, assuming attrition was random, the indicative MDES estimate is 0.19 sds.

Therefore, following the updated power analysis, the recommended sample size for the evaluation of the Tavistock MBT-PP programme is reduced from 350 families (700 CYP) to be 250 families (350 CYP).

Analysis

Research questions were operationalised as follows:

RQ1 Does MBT-PP (compared to TAU) delivered to parents experiencing IPC lead to lower externalising and internalising behaviours in children aged 8-14 (as measured by the SDQ total 'difficulties' scale)?

This splits into two separate RQs (SDQ total difficulties for mothers and for fathers).

RQ1a Does MBT-PP (compared to TAU) delivered to parents experiencing IPC lead to lower externalising and internalising behaviours in children aged 8-14 as measured by the mother's SDQ total 'difficulties' scale? – PRIMARY OUTCOME RQ1

RQ1b Does MBT-PP (compared to TAU) delivered to parents experiencing IPC lead to lower externalising and internalising behaviours in children aged 8-14 as measured by the father's SDQ total 'difficulties' scale? – SECONDARY OUTCOME RQ1

RQs 2-8 inclusive also all examine secondary outcomes, and, apart from those where the outcome variable comes from CYP rather than parents (RQ2 regarding child wellbeing and RQ4 regarding child perception of IPC), they split into a) maternal report and b) paternal report, as per RQ1.

RQ2 Does MBT-PP (compared to TAU) delivered to parents experiencing IPC lead to higher wellbeing in children aged 8-14 (as measured by the Stirling Children's Well-being Scale)?

RQ3 Does MBT-PP (compared to TAU) delivered to parents experiencing IPC lead to lower IPC reported by parents (as measured by the O-Leary-Porter Scale)?

RQ3a Does MBT-PP (compared to TAU) delivered to parents experiencing IPC lead to lower IPC reported by mothers (as measured by the O-Leary-Porter Scale)?

RQ3b Does MBT-PP (compared to TAU) delivered to parents experiencing IPC lead to lower IPC reported by fathers (as measured by the O-Leary-Porter Scale)?

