The analysis described in this plan follows YEF analysis guidance¹. An Intention to Treat (ITT) approach will be taken whereby CYP are identified as members of the intervention or control group solely based on their random allocation and regardless of whether their parent(s) participate in the intervention or not. The ITT approach best preserves random allocation. This means that the only difference between the two group (of families/parents) is that one group received the Tavistock MBT-PP programme and the other groups (TAU) did not. All other differences between these groups are (fixed to be) random at baseline and, assuming zero attrition, this assumption is maintained at outcome. It is the ITT analysis of the primary outcome (mothers reported SDQ total difficulties score) that this clustered RCT is statistically powered to detect. Specifically and assuming zero attrition, if a difference between the intervention and control group is observed to be 0.17 sds or higher, this would represent evidence that participation in the Tavistock programme caused this positive (or negative) impact within pre-specified levels of statistical significance ($p < 0.05$, two-tailed) and statistical power (0.80 or higher). As detailed below, following the ITT analysis of the primary outcome, missing data and Compliers Average Causal Effect (CACE) analyses will be undertaken.

An ITT approach will also be used for analyses of secondary outcomes. Follow-on analyses of the primary outcome will estimate the Compliers Average Causal Effect (CACE); the impact of the programme for CYP located in families/parents known to have engaged in the MBT-PP programme as was intended (see below).

All analyses will be undertaken using STATA v18. Specifically, parameter estimates will be obtained using the 'mixed' suite of commands in the STATA software. For primary and secondary outcomes, pre-test covariates will be included at both CYP and cluster (family) levels. These will be centred as recommended by Hedges & Hedberg (2007 & 2013) and Konstantopoulos (2008). Specifically, at the CYP level, scores will be centred around the cluster (family/parent) mean and at the family/parent level the cluster(family) means will be centred around the overall cluster-level grand mean. Other than the constant term, centring

¹ <https://youthendowmentfund.org.uk/resources-for-evaluators/>

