If the assumption of measure invariance is upheld, we will look to compare latent means across group with a particular focus on the mentalising latent variables as these are the key targets of the MBT intervention. This would be undertaken by restricting the models to have equal means in the mentalising latent variables and then conducting likelihood ratio tests to compare this constrained model with the model where the means are free to vary. If the likelihood ratio test is not significant then this would suggest that groups do not differ in terms of these latent means. We would also compare the regression coefficients from the mentalising latent variables to the anger expression latent variable in a similar way.

We will first utilise the above method to test a model featuring post-intervention SDQ-TD score (mothers) as the final endogenous variable in the causal chain. We will then test the same models with child well-being score at post-intervention as the final endogenous variable (figures 3 and 4). We will repeat this whole process using fathers' SDQ-TD scores. We will run these SEM models even in the absence of a main effect on each final endogenous variable, because it is possible to detect indirect effects in the absence of a direct effect, and indeed important to do so to provide information as to why the main effect is present or not (O'Rourke & Mackinnon, 2018).

Additionally, if there are sufficient responses from the three month follow-up testing for the primary (child internalising and externalising behaviours) and secondary (child psychological well-being) measures we will re-test the models in Figures 1 & 3 (and if possible Figures 2 & 4) but with replacing the post-intervention measures of these primary and secondary outcome with the three-month follow-up measures of these variables. This potentially enables us to test whether changes to mentalising, anger expression, interparental conflict and parenting style at time 2 predicts child behaviour and well-being at follow-up and thus potentially further supporting any causal relationships established from the post-intervention SEM modelling.

Figure 3. Proposed causal model for SEM analysis with the secondary outcome measure of child psychological well-being.

[figure not shown]
[figure not shown]

Figure 4. Proposed causal model for SEM analysis for separated parents with the secondary outcome measure of child psychological wellbeing, including the parental emotional adaptation measure.

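### A non-significant likelihood ratio test on latent mentalising should be reported as inconclusive, not as suggesting that the arms do not differ

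*SAP*

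**What the plan says.** The rule is in the SAP, section Testing the theory of change mechanisms. If measurement invariance holds, latent means are compared across arms "with a particular focus on the mentalising latent variables as these are the key targets of the MBT intervention". The method is "restricting the models to have equal means in the mentalising latent variables and then conducting likelihood ratio tests" against a model in which the means are free. The reading of a null is then set: "If the likelihood ratio test is not significant then this would suggest that groups do not differ in terms of these latent means". The next sentence extends the approach: "We would also compare the regression coefficients from the mentalising latent variables to the anger expression latent variable in a similar way".

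The section says that the initial models use post-intervention measures, and it describes no baseline adjustment. It gives no confidence interval for the latent mean difference, no smallest difference of interest and no power.

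On power, the SAP's Analysis section is explicit: "It is the ITT analysis of the primary outcome (mothers reported SDQ total difficulties score) that this clustered RCT is statistically powered to detect".

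**The concern.** Failing to reject equal means does not show that the means are equal. How far a null can be trusted depends on what the test could have detected, and the plan does not address this. The precision behind the trial's 0.17 SD sensitivity comes from baseline SDQ scores, which this test does not use.

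The theory of change starts with mentalising, and the SAP will run these models even without a main effect, in order to help explain why an effect is or is not present. A null misread at this step could become part of the explanation of the trial result. There is a precedent: the protocol's background section reports that in the feasibility study of MBT-PP "the study failed to detect a significant difference in the parents' ability to mentalise according to the quantitative measures", while its qualitative findings pointed to subtle shifts. A second inconclusive null could be written up as no difference.

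**Working it through.** **1. Reproduce the SAP's own figure (primary outcome).** Inputs from the SAP's Sample size calculations: 1.4 CYP per family, ICC 0.27, R² 0.61 (family) and 0.75 (CYP), m = 6, P = 0.5.

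MDES = M × 2 × √[0.27(1 − 0.61)/J + 0.73(1 − 0.75)/(1.4J)], with M = t(0.975) + t(0.80) on J − 8 df (about 2.81).

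| Families | Computed | SAP |
|---|---|---|
| 250 | 0.173 | 0.17 |
| 225 (10% attrition) | 0.182 | 0.18 |
| 200 (20% attrition) | 0.193 | 0.19 |

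The SAP's figures reproduce. They depend on the two R² values, which belong to mothers' SDQ total difficulties.

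**2. Inputs for the latent-mean test.**
- From the documents: 250, 225 or 200 families in total (125 to 100 per arm); subscale alphas 0.69, 0.77 and 0.75 (Protocol, Secondary outcomes, PRFQ entry).
- Assumed: alpha 0.05 (the SAP states it for the primary analysis); one independent record per parent; full invariance; factor correlation 0 to 0.5.
- Illustrative: d = 0.2 SD, from the SAP's aim to "detect an MDES of 0.20 sds or higher" on mothers' SDQ.
- Not stated: whether the three means are tested separately (1 df) or jointly (3 df). Both are shown.

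**3. Chance of missing 0.2 SD on one subscale.** Noncentrality = (N/4) × d² × reliability, referred to a noncentral chi-square. For example, N = 250 and reliability 0.77 give 62.5 × 0.04 × 0.77 = 1.925, a 1 df miss rate of 72%. The joint-test columns take uncorrelated factors.

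| Families | 1 df, rel. 0.77 to 0.69 | 3 df, rel. 0.77 to 0.69 | 1 df, error-free | 3 df, error-free |
|---|---|---|---|---|
| 250 | 72-74% | 81-83% | 65% | 77% |
| 225 | 74-76% | 83-84% | 68% | 79% |
| 200 | 76-78% | 84-86% | 71% | 81% |

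Factor correlations up to 0.5 bring the 3 df figures down to no lower than 77%.

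**4. All three subscales shift (3 df).** Noncentrality = (n/2) k′(Φ + E)⁻¹k, with n per arm, k the vector of shifts, Φ the factor correlation matrix and E diagonal with entries (1 − α)/α = 0.45, 0.30, 0.33 (α here being Cronbach's alpha).

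| Factor correlation | 0.2 SD, 250 families | 0.2 SD, 200 families | 0.5 SD, 200 families |
|---|---|---|---|
| 0 | 52% | 61% | under 1% |
| 0.3 | 66% | 72% | 3% |
| 0.5 | 71% | 76% | 7% |

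**5. Interval width.** Half-width = 1.96 × √[(2/n)(1 + E)]. Best case, n = 125 and E = 0.30: 1.96 × √(0.016 × 1.30) = 0.28 SD. Worst case, n = 100 and E = 0.45: 1.96 × √(0.020 × 1.45) = 0.33 SD. An interval this wide cannot lie wholly inside ±0.20 SD.

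**6. The baseline-adjusted alternative.** For 0.2 SD on an observed score with an assumed baseline R² of 0.25 to 0.49, power = Φ(√[(N/4)(0.04)/(1 − R²)] − 1.96), where Φ is now the normal distribution function. N = 200 and R² = 0.25 give 37%; N = 250 and R² = 0.49 give 60%. This is better than the latent test, though still short of 80%.

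**The case against.** The strongest reply is that the trial's formal answer on mentalising lies elsewhere. RQ6a and RQ6b ask about it directly. SAP Table 4 lists all three PRFQ subscales, for mothers and fathers, as secondary outcomes, and equation 3.0 adjusts each for baseline and the minimisation variables. The protocol calls the mediation models exploratory, and parent interviews also cover change in mentalising. All of this stands. A reader might infer that the plan will report the first causal step as absent in most trials where it is present. The documents do not support that, because the latent-mean test sits beside a separate adjusted estimate. That estimate does not repair the rule for reading the latent test, however, and Presentation of outcomes spells out an effect size and interval only for mothers' SDQ.

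The wording is also tentative: it says what a null would suggest, not what it proves. That is fair, but the inference still runs from non-significance to no difference.

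Next, 0.2 SD was chosen for child outcomes. A reader might take it as the effect the trial seeks on mentalising; neither document says so. Nor is 70% a floor for the miss rate: section 4 of the working gives 52-61% when all three subscales shift and are uncorrelated, and large shifts on several are rarely missed.

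Finally, the SAP does not specify the rows of the SEM data set, and the path diagrams were not available for this check. One record per parent is therefore an assumption. Using 350 CYP as rows would only repeat a parent's mentalising score across siblings.

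**Conclusion.** The point holds as a matter of interpretation in an exploratory mechanism analysis. Under the SAP's rule, a null that carries little information would be read as suggesting no difference in the intervention's key target. Under the stated assumptions, a 0.2 SD shift on one subscale would be missed about 72-86% of the time (65% in the most favourable single-subscale case), and about 52-76% of the time if all three shift. The 95% CI half-width is about 0.28-0.33 SD.

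These rates describe an illustrative effect size and should be quoted with their assumptions. The primary analysis and its conclusion are unaffected, and nothing in the documents claims that the 0.17 SD sensitivity applies to this test.

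**What to change.** Replace the sentence in the SAP with:

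> *Differences between arms in latent means, and in the mentalising-to-anger coefficients, will be reported as standardised estimates with 95% CIs. A non-significant likelihood ratio test will be reported as inconclusive, not as evidence that the groups do not differ, and will be read alongside the baseline-adjusted PRFQ secondary outcome estimates.*

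The baseline-adjusted PRFQ analyses should be the main basis for statements about mentalising. An equivalence margin of ±0.20 SD should not be added: this sample cannot meet it, and it would supply no margin for the regression coefficients.

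The cost is a wording change, best made before the SEM is run. The planned scalar-invariance model already yields the latent mean estimates and their intervals, and no change to data, design or sample is needed. The downside is that the SEM will not support a claim of no difference.

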- b) The acceptability of the referral pathways and consent and randomisation procedures to participants (indicated by drop out rates at these points)
- c) Whether there are any signs of problematic attrition (e.g. that might indicate that the research processes or interventions are not acceptable to participants)

- d) How the estimates used for the sample size calculation should be adjusted in light of data.

These aims inform the progression criteria (Appendix A), which utilise a red/amber/green classification system, whereby amber or red indicate that mitigations are required prior to progression.

Additional aims for the pilot study are:

- e) To pilot the data collection methods (including examining completion time and parent views on completing measures)
- f) To pilot data linking processes
- g) To seek early evidence supporting the Theory of Change
- h) To explore the relationship between parents' SDQ reports

Outcome measures

Certain features of the trial design mean that there is not a wide range of measures to choose from for many of our constructs. These include the age range of CYP targeted; 8-14 years is a wide age range and spans multiple developmental stages. Another feature that makes measure options limited is the fact that families may be intact or separated. Measures of IPC are typically intended for only one of these groups and are not appropriate for both. Finally, some of our constructs are only recently identified in the literature, or simply have not received a similar level of research attention as others, which means that only one measure exists (to the very best of our knowledge). Despite these challenges, we have selected a set of measures that are appropriate for the target population and have good psychometric properties.

All measures will be completed at baseline, post-intervention, and 3 month follow up.

Primary outcome

- a) The Strengths and Difficulties Questionnaire (SDQ; Goodman, 1997)

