Table 4 above lists a total of 35 secondary outcomes. For all 35 secondary outcomes, an ITT approach will be taken.

For the analysis of all secondary outcomes, an estimate of impact will be obtained from a hierarchical linear model described in equation 3.0:

$$[3.0] \quad Y_{ij} = \beta_0 + \beta_1 T_j + \beta_2 (X_{ij} - \bar{X}_j) + \beta_3 (\bar{X}_j - \bar{X}) + \beta_{4..7} [MIN DUM]_j + \vartheta_j + \varepsilon_{ij}$$

Where:

- Y_{ij} is secondary outcome score for CYP i in family j at T2 (16 weeks following minimisation).
- T_j is the family-level group identifier which will take the value 1 (=MBT) or zero (=TAU)
- β_1 is the coefficient that estimates the difference between the MBT and TAU groups adjusted for baseline scores and mimimisation variables; i.e. $(MBT - TAU)_{adjusted}$
- X_{ij} is the baseline score for the secondary outcome for CYP i in family j at T1/baseline centred around \bar{X}_j , the family-level mean (i.e. $(X_{ij} - \bar{X}_j)$)
- \bar{X} is the family-level grand mean for the secondary outcome and used to centre \bar{X}_j , the family-level mean (i.e. $\bar{X}_j - \bar{X}$)
- $[MIN DUM]_j$ is the collection of four family-level dummy variables used in the minimisation; ages of CYP in family (two variables); whether one parent was not White British (one variable) and relationship status (one variable).
- $\beta_{4..7}$ are the coefficient estimates for the four family-level dummy variables.
- ϑ_j and ε'_{ij} are random effects that remain at the school and pupil levels and are assumed to be distributed normally in the population with zero means, variances σ_c^2 and τ_c^2 respectively.

Table 6 summarises the ITT analysis for the fathers SDQ-TD secondary outcome as an example, a similar approach will be used for all secondary outcomes at T2.

Table 6. Example analysis model for fathers SDQ-TD primary outcome (RQ1b)

Analysis and Sample	Level 1 (CYP) Covariates	Level 2 (Family) Covariates	Outcome Variable

Empty model			CYP level fathers SDQ-TD (raw) score at T2 (16 weeks following minimisation)
Final Model	Fathers SDQ-TD score at T1/baseline (Centred around family mean)	Mean fathers SDQ-TD score at T1/baseline (Centred around grand mean) Group membership (MBT or TAU) Four Minimisation Variables: CYP ages (2), parental ethnicity (1), relationship status (1).	CYP level fathers SDQ-TD (raw) score at T2 (16 weeks following minimisation)

Subgroup analyses

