Null/Empty Models Two Subsamples: Pilot & Stage 2 evaluations.			CYP level mothers SDQ-TD (raw) score at T2 (16 weeks following minimisation)
Subgroup Impact Models Two Subsamples: Pilot & Stage 2 evaluations.	Mothers SDQ-TD score at T1/baseline (Centred around family mean)	Mean mothers SDQ-TD score at T1/baseline (Centred around grand mean) Group membership (MBT or TAU) Four Minimisation Variables: CYP ages (2), parental ethnicity (1), relationship status (1)	CYP level mothers SDQ-TD (raw) score at T2 (16 weeks following minimisation)

Longitudinal follow-up analyses

The T3 3 month follow up data provides 18 of the secondary outcome variables (see Table 4). As specified above, these will be subjected to the same analyses as the primary outcome variable.

Testing the theory of change mechanisms

To examine the causal mechanisms proposed in the theory of change we will undertake multigroup structural equation modelling (SEM) comparing the model in Figure 1 across the MBT and TAU groups. The initial model will be undertaken using the post-intervention measures of the variables included in Figure 1.

Figure 1. Proposed causal model for SEM analysis with child internalising and externalising behaviours (mothers' SDQ-TD) as the final latent variable in the causal chain on post-intervention measures.

[figure not shown]
[figure not shown]

Figure 2. Proposed causal model for SEM analysis for separated parents, including the parental emotional adaptation measure.

Using the data from separated families only, we will also test the model in Figure 2, which treats emotional adaptation to relationship dissolution as an additional mediator, alongside anger expression. Again, this will be undertaken using the post-intervention measures.

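### The theory-of-change SEMs contain no baseline scores, so their within-arm mediator-to-outcome paths relate levels and do not support the SAP's wording about changes and causal support

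*SAP*

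**What the plan says.** The section of the SAP on testing the theory-of-change mechanisms specifies a multigroup SEM by arm, with parameters estimated separately in each arm. On the data to be used it says: "The initial model will be undertaken using the post-intervention measures of the variables included in Figure 1". For the model restricted to separated parents it says: "Again, this will be undertaken using the post-intervention measures". The caption of Figure 1 also refers to post-intervention measures.

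If there are enough three-month responses, the models are refitted by "replacing the post-intervention measures of these primary and secondary outcome with the three-month follow-up measures of these variables". The mediators stay at T2. The SAP says this version may "test whether changes to mentalising, anger expression, interparental conflict and parenting style at time 2 predicts child behaviour" and well-being, and may add to any causal relationships found in the T2 models.

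Mentalising is compared between arms by constraining the latent means to be equal and "conducting likelihood ratio tests to compare this constrained model with the model where the means are free to vary". The mentalising-to-anger coefficients are compared in a similar way.

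No step names a T1 score. Yet the protocol, under Outcome measures, says "All measures will be completed at baseline, post-intervention, and 3 month follow up", and the SAP's impact models do use baseline: "For primary and secondary outcomes, pre-test covariates will be included at both CYP and cluster (family) levels".

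**The concern.** A path from a T2 mediator to a T2 or T3 child outcome, fitted with no T1 scores, relates the level of one to the level of the other. The protocol's rationale states that inter-parental conflict is related to poorer child adjustment. Families with more conflict before the trial may therefore already have children with higher SDQ scores. If both measures are stable, that association carries forward into the later path. Moving only the outcome to T3 does not remove it.

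Randomisation does not protect these paths, because within an arm they are observational. The SAP will run the models even if there is no main effect, partly to explain why. It also says that if measurement invariance fails, each arm will be modelled alone with no comparison of parameters across arms. In that case only the unprotected paths remain, and the SAP's wording would invite a reader to take them as evidence of mechanism.

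**Working it through.** **Reference figure.** The documents give no power or error rate for the SEM. The pilot inputs used below come from the SAP's sample size section, so I first checked that they reproduce its MDES. With J = 250, m = 6, n = 1.4, P = 0.5, ICC = 0.27, family R² = 0.61 and CYP R² = 0.75, equation 1.0 has 242 degrees of freedom and a multiplier of about 2.81:

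2.81 × 2 × √(0.27 × 0.39/250 + 0.73 × 0.25/350) = 0.173, against the stated 0.17.

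**Inputs for the path check**
- 125 families per arm (SAP Table 2), with one child and one reporter per family for simplicity.
- SDQ stability T1 to T2, implied by the pilot values: residual variance = 0.27 × (1 − 0.61) + 0.73 × (1 − 0.75) = 0.288, so r = √(1 − 0.288) = 0.84.
- Mediator stability r_M of 0.5 to 0.7. This is assumed. It borrows the protocol's pre-post range, which was stated for the SDQ power calculation. No value is given for any mediator.
- T1 mediator-SDQ correlation r_0 of 0.2 to 0.4. This is assumed and is not in the documents.
- True effect of mediator on outcome: zero.

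**Formula.** The expected T2 correlation is r = r_M × r_Y × r_0. The chance of two-sided significance at 5% is approximately Φ(z − 1.96) + Φ(−z − 1.96), where z = atanh(r) × √122.

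| r_M | r_Y | r_0 | expected r | z | chance significant |
|---|---|---|---|---|---|
| 0.5 | 0.84 | 0.2 | 0.084 | 0.93 | 15% |
| 0.5 | 0.84 | 0.3 | 0.126 | 1.40 | 29% |
| 0.7 | 0.84 | 0.3 | 0.176 | 1.97 | 50% |
| 0.7 | 0.84 | 0.4 | 0.235 | 2.65 | 75% |
| 0.5 | 0.60 | 0.3 | 0.090 | 1.00 | 17% |
| 0.7 | 0.60 | 0.3 | 0.126 | 1.40 | 29% |

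Separate simulations agree with the formula. Over the r_Y = 0.84 range they gave 14% to 77%. With T1 mediator and T1 outcome added, the rate was 4% to 6% in every cell. The last two rows use an assumed outcome stability of 0.6, as might apply at T3, for which the documents give no value. Simulation put those two cells at about 17% to 28%.

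**Measurement error.** With reliabilities of 0.75 and 0.80, r_0 = 0.3 and stabilities from 0.5/0.5 to 0.7/0.84, the rate was 10% to 33%. That is lower than with error-free scores but still above 5%.

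**Between-arm check.** In the same no-effect simulations, the difference between arms in the path coefficient was significant in about 4% to 6% of samples. The carried-over association is expected equally in both arms and cancels in the comparison.

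**Mentalising means.** For one observed score per family and 250 families, SE = √(4(1 − R²)/250) and MDES is about 2.80 × SE.
- No baseline: SE 0.126, MDES 0.35, power at 0.30 SD 66%.
- R² = 0.25: MDES 0.31, power 78%.
- R² = 0.49: MDES 0.25, power 91%.

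These figures are indicative only. The planned test is a likelihood-ratio test on latent variables, and the documents give no pre-post correlation for the PRFQ.

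**The case against.** The strongest reply is that a path inside one arm is not yet a mechanism of MBT-PP. A mechanism also needs an effect of allocation on the mediator, and the tests the SAP spells out are between arms. This stands. Randomisation makes the T2 comparison of latent means a valid test of the effect on mentalising, and comparing coefficients between arms is not inflated. A reader might infer that the SEM cannot show any effect on a mediator, or that a false mechanism will often be reported. The documents support neither. The first confuses the arm-to-mediator effect with the mediator-to-outcome path. The second depends on correlations they do not give.

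A reader might also infer that the trial loses power for mentalising. It does not lose it overall. The three PRFQ subscales, for mothers and for fathers, are secondary outcomes in SAP Table 4, and "For the analysis of all secondary outcomes, an estimate of impact will be obtained from a hierarchical linear model described in equation 3.0", which includes the baseline score. Only the SEM comparison is less precise.

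Further limits also stand. The protocol calls the mediation models exploratory, and the SAP's sentence on changes is hedged. The SDQ stability rests on 61 children in 43 families. The calculation uses one mediator, whereas the planned models have several, and the path diagrams are not available here. So the percentages illustrate the problem and are not predictions for the planned models.

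None of this answers the central point. The hedged sentence still attributes to the model a test of change that it does not contain.

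**Conclusion.** The point holds for the within-arm mediator-to-outcome paths. As the text and captions describe them, the SEMs relate T2 levels to T2 or T3 levels, so the statements about changes and further causal support do not follow. This part needs no numerical assumption.

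The size is conditional. For a mediator with no effect, a single within-arm path would be significant in about 14% to 77% of samples under the stated inputs, or about 17% to 28% at a baseline correlation of 0.3 if outcome stability were 0.6. It would be about 5% with both T1 scores in the model. If mediator and outcome were uncorrelated at baseline, there would be no inflation.

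The primary and secondary impact estimates are unaffected. The change should be made because the mechanism analysis is a stated aim of the trial and the remedy uses data already planned.

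**What to change.** In every SEM, regress each T2 mediator on its own T1 score and each T2 or T3 child outcome on its own T1 score. Include the T1 mediator scores in the child-outcome equation, or let the T1 scores covary. Observed T1 scale scores are sufficient. Compare mentalising means between arms conditional on T1 mentalising.

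If this is not done, remove the reference to changes and the statement about further supporting causal relationships, and report the paths as exploratory associations.

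The cost is SAP wording and a slightly larger model. Cases without a T1 score are lost, but equations 2.0 and 3.0 already require one. Baseline adjustment will not remove confounding that arises after baseline, or bias from the same parent reporting both mediator and outcome, and the SAP should say so.
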